5.2.2. Laboratory Variables for the Assessment of Efficacy

Efficacy in this study includes the following lipid parameters:

- Fasting TG levels
- Non-HDL-C levels

- TC levels
- ApoC3, ApoB48, ApoB100, NMR-determined particle size and number (biomarkers of TG-rich lipoprotein metabolism)

These laboratory variables are relevant to the characterization and disease mechanisms of patients with HTG.

5.2.3. Clinical Outcome Assessments

The following clinical outcome assessment (COA) will be completed by the patient:

- A single-item assessment on presence of abdominal pain
- The HAP-Pain Questionnaire

5.3. Safety Variables

The safety variables in this study include:

- TEAEs
- Vital signs
- Physical examination
- Electrocardiogram (ECG)
- Routine safety laboratory tests (hematology, chemistry, urinalysis, and pregnancy testing [for women of childbearing potential or WOCBP])
- Concomitant medications and treatments

5.4. Pharmacokinetic Variables

The pharmacokinetic variables consist of the concentrations of total evinacumab and total ANGPTL3 in serum at each time point (both pre-dose and end-of-infusion samples). These sampling time points are specified in [Table 1](#).

5.5. Immunogenicity Variables

The immunogenicity variables are ADA status, titer, NAb status, and time point/visit. Samples in this study will be collected at the clinic visits specified in [Table 1](#) and [Table 2](#).

5.6. Pharmacodynamic and Other Biomarker Variables

The pharmacodynamic (PD) variables in this study are high-density lipoprotein cholesterol (HDL-C) and LDL-C.

ApoC3, ApoB48, ApoB100, and NMR-determined particle size and number are biomarkers of TG-rich lipoprotein metabolism and are also efficacy variables in this study.

6. STUDY DESIGN

6.1. Study Description and Duration

This is a phase 2b, multicenter, international, randomized, placebo-controlled study intended to demonstrate that evinacumab can prevent recurrent AP in patients with HTG and a recent history of HTG-associated AP.

Approximately 120 adult patients will be randomized 1:1 to receive evinacumab or matching placebo. A study schematic is provided in [Figure 1](#).

The study consists of 3 periods: a screening period, a DBTP, and a safety follow-up period. The screening period of up to 28 days will determine participant eligibility and will include an evaluation of prior episodes of HTG-associated AP, genotyping to exclude patients with FCS due to LoF mutations in LPL, and a measurement of fasting TG level. Patients must have baseline fasting TGs >880 mg/dL and a history of HTG-associated AP within 24 months of screening or they must have baseline fasting TGs >500 mg/dL if they have had 2 or more episodes of HTG-associated AP within 24 months of screening or if they have had baseline fasting TG values >500 mg/dL and documented fasting TG values >1000 mg/dL with a history of HTG-associated AP within 24 months of screening to be enrolled in the study.

[figure not shown]
Patients who fulfill all the eligibility criteria will be randomized and receive their first dose of assigned study drug on day 1, with subsequent doses administered approximately Q4W during the 52-week DBTP. This will be followed by an off-drug follow-up period of 20 weeks.

Every effort will be made to keep patients in the study and to collect the week 52 visit data, even if study drug administration has been discontinued for the patient.

Efficacy will be assessed by measuring the number of patients with at least 1 independently adjudicated positive event of AP over 52 weeks of treatment with evinacumab versus placebo. The study will have an independent committee to adjudicate these episodes in accordance with clinical standards for diagnosis of AP (see Section [5.2.1](#)). Efficacy will also be assessed by clinical laboratory evaluation of lipid levels at pre-specified time points throughout the study.

Safety will be assessed throughout the study by comparing the frequency and severity of adverse events (AEs) between the evinacumab and placebo groups, as well as evaluating abnormal laboratory findings, ECG findings, and ADA and NAb assessments.

Figure 1: Study Flow Diagram

Screening (Day -28 to -1)

The screening period may last up to 28 days and consists of 1 visit. During the screening period, all patients will undergo the informed consent process and standard screening procedures. Laboratory assessments used to determine eligibility may be repeated once during the screening period. The fasting TG measurement can be repeated once for values >500 mg/dL but <880 mg/dL.

A mandatory sample for DNA isolation will be obtained for patients who do not have documentation of prior genetic testing in order to confirm the absence of FCS due to homozygous or compound heterozygous LoF mutations in *LPL*. For these patients, the results of the screening FCS genotyping confirming no homozygous or compound heterozygous LoF mutations in *LPL* must be available before the patient can be enrolled in the study.

Patients who have screen-failed are not eligible for rescreening, unless rescreening is discussed and agreed with the medical monitor.

After confirmation of eligibility, patients will proceed to visit 2 for randomization.

Double-Blind Treatment Period (Day 1 to Day 365)

Principal investigators, study site personnel, study patients, and the Regeneron study team will all be blinded to treatment during the DBTP.

Randomized patients will receive either evinacumab administered IV at a dose of 20 mg/kg IV or matching placebo Q4W (± 4 days) during the DBTP. On dosing days, all assessments and lab samples (including urine or serum pregnancy tests for WOCBP) should be performed before the dose of study drug is administered. All samples should be collected following at least an 8-hour fast. Medications are permitted to be taken with water as medically indicated. Electrocardiograms should be performed before blood is drawn. Additionally, vital signs should be measured, and AEs monitored pre-dose, at the end of study drug infusion, and at 30 minutes and 60 minutes post-end of infusion. Patients will be closely monitored for a minimum of 60 minutes after IV administration of evinacumab or matching placebo.

Efficacy and safety procedures, including a standard lipid panel, dietary and alcohol use review, and the completion of a pain questionnaire will be performed as outlined in the Schedule of Events ([Table 1](#)).

Serum samples for the determination of total evinacumab and total ANGPTL3 should be collected prior to AND at the end of infusion of study drug (within 30 minutes from the end of infusion).

Serum and plasma samples will be collected for analysis of additional biomarkers, including specialty lipid measurements, and will also be collected for measurement of ADA and NAb.

Off-Drug Treatment Follow-up Period (Day 366 to Day 700 /End of Study)

Patients will be monitored for 20 weeks after the last dose of study drug with 2 in-clinic visits. Efficacy and safety procedures will be performed as outlined in the Schedule of Events.

Throughout the Study

Patients will adhere to their diet, and submit to a dietary review and an alcohol intake review at each visit. Patients will be reminded to maintain a stable diet and refrain from drinking more than 1 serving per day of an alcoholic beverage.

Patients will also be reminded at visits and during phone calls to adhere to a highly effective birth control method. Pregnancy status of female patients of childbearing potential will be monitored throughout the study and for 20 weeks post the last dose of study drug.

COVID-19

Recognizing that the “Coronavirus Disease 2019” (COVID-19) pandemic will have an impact on the conduct of clinical trials, the sponsor does not intend to screen any patients in this study until the impact of the COVID-19 pandemic is deemed manageable and no longer interfering with the conduct of trials at individual sites, and patients can safely participate in this study. Until then, the sponsor plans to obtain approvals from health authorities/ECs to enable initiation of study sites for this study, as allowed by local laws and regulations.

In light of the public health emergency related to COVID-19, the continuity of clinical study conduct and oversight may require implementation of temporary or alternative mechanisms. Examples of such mechanisms may include, but are not limited to, any of the following: phone contact, virtual visits, telemedicine visits, online meetings, non-invasive remote monitoring devices, use of local clinic or laboratory locations, and home visits by skilled staff. Additionally, no waivers to deviate from protocol enrollment criteria due to COVID-19 will be granted. All temporary mechanisms utilized, and deviations from planned study procedures, are to be documented as being related to COVID-19 and will remain in effect only for the duration of the public health emergency.

6.1.1. End of Study Definition

The end of study is defined as the date the last study participant completes the last study visit, withdraws from the study, or is lost to follow-up (ie, the participant can no longer be contacted by the investigator).

6.2. Planned Interim Analysis

An interim analysis is planned when approximately 50% (N=60) of patients have completed the DBTP. This will consist of the final data contributing to the analysis of the applicable variables up to the week-52 visit for these patients. The efficacy analyses will be performed up to the week-52 visit for these patients and will be descriptive in nature. The safety analysis will be performed for these patients on all safety data collected and validated at the time of the interim analysis. A small alpha adjustment of 0.001 has been made to account for this treatment-unblinded interim, since the sponsor does not plan to stop the study early for evinacumab treatment benefit. Therefore, the significance level for the final efficacy analysis will be 0.049.

The purpose of this interim analysis is administrative, specifically to aid in planning of future studies. The interim statistical analysis will be performed external to Regeneron with the intent to reduce data bias in the patients ongoing in the DBTP at the time of the interim. Interim analysis summary results will be provided to Regeneron senior management only. The interim analysis process, the measures used to protect the blind and the integrity of the study, the communication plan, and the confidentiality agreement will be described in a separate document.

A description of the statistical methods to be employed is in Section 11.5.1, and blinding implications are discussed in Section 8.6.

6.3. Study Committees

The Independent Data Monitoring Committee (IDMC) for the evinacumab program will be utilized. In addition, a separate independent committee (APAC) consisting of clinical specialists will be formed for adjudicating cases of AP to ensure a clinically accepted and consistent diagnosis for this primary endpoint. Every effort will be made to maintain the same group of physician reviewers for adjudication.

7. SELECTION, WITHDRAWAL, AND REPLACEMENT OF PATIENTS

7.1. Number of Patients Planned

Approximately 120 patients (randomized 1:1, evinacumab: placebo).

7.2. Study Population

7.2.1. Inclusion Criteria

A patient must meet the following criteria to be eligible for inclusion in the study:

1. Adults 18 to 80 years of age without FCS due to LPL loss of function mutations
2. Documented history of 1 HTG-associated AP episode within 24 months of screening (can be determined by study investigator; does not need to be confirmed by independent adjudication committee) and.
3. Fasting serum TG value >880 mg/dL (10 mmol/L) determined during the screening period. Triglyceride measurement can be repeated once for values >500 mg/dL (5.6 mmol/L) but <880 mg/dL (10 mmol/L)

OR

Fasting serum TG value >500 mg/dL (5.6 mmol/L) determined during the screening period in patients with a history of 2 or more HTG-associated AP episodes within 24 months of screening

OR

Fasting serum TG value >500 mg/dL (5.6 mmol/L) determined during the screening period and a documented fasted serum TG value >1000 mg/dL (11.3 mmol/L) and a history of 1 or more HTG-associated AP episode(s) within 24 months of screening.

4. Stable dose of lipid-lowering therapy (≥ 8 weeks) and willingness to maintain a stable regimen throughout the study
5. Body mass index ≥ 18.0 and $\leq 45.0 \text{ kg/m}^2$
6. Compliance with a stable diet and exercise regimen at screening and willingness to continue the diet through the end of the study
7. Willing and able to comply with clinic visits and study-related procedures
8. Provide informed consent signed by study patient or legally acceptable representative
9. Able to understand and complete study-related questionnaires

7.2.2. Exclusion Criteria

A patient who meets any of the following criteria will be excluded from the study:

1. Hospitalization for AP within 4 weeks of screening

2. Known genetic FCS defined as homozygous or compound heterozygous LoF mutations in LPL, as documented by prior genotype result or determined from FCS genotyping at screening (see Section 9.2.7).
3. Symptomatic gallstone disease within 6 months prior to screening. Incidental and/or asymptomatic gallstones are permitted. Patients with symptomatic gallstone disease in the past 6 months who have undergone cholecystectomy >3 months prior to screening are permitted.
4. Use of any medication or nutraceutical known to alter serum lipids which has not been part of a stable therapeutic regimen for at least 8 weeks, and there are no plans to change the regimen during the study
5. Presence of any clinically significant, uncontrolled endocrine disease known to influence serum lipids, including but not limited to:
 - a. Newly diagnosed (within 3 months) diabetes by medical history, including screening value glycosylated hemoglobin (HbA1c) >6.5% without a prior history of diabetes
 - b. Diabetes with HbA1c >10.0%
 - c. Thyroid disease with thyroid-stimulating hormone (TSH) <lower limit of normal (LLN) or >1.5x ULN
 - d. Thyroid replacement therapy that has not been stable for at least 12 weeks

Note: For laboratory values, 1 repeat measurement is allowed. Other laboratory values that meet the inclusion/exclusion criteria do not need to be repeated.

6. Use of estrogen or testosterone therapy unless the regimen has been stable in the past 6 weeks and there are no plans to change the regimen during the study
7. Any clinically significant abnormality identified at the time of screening that, in the judgment of the investigator or any sub-investigator, would preclude safe completion of the study or constrain endpoints assessment; eg, major systemic diseases, patients with short life expectancy, or considered by the investigator or any sub-investigator as inappropriate for this study for any reason, including but not limited to:
 - a. Deemed unable to meet specific protocol requirements, such as scheduled visits
 - b. Deemed unable to tolerate injections, as per the patient or the investigator
 - c. Part of a vulnerable population such as the institutionalized
 - d. Presence of any other conditions (eg, geographic or social), either actual or anticipated, that the investigator feels would restrict or limit the patient's participation for the duration of the study
8. Laboratory findings (for the reason that patients with these findings, who have a higher likelihood of liver, muscle, or kidney adverse events regardless of treatment assignment, are expected to be rare, they may not be evenly distributed across treatment groups and thus may confound the analysis of safety):
 - a. Estimated glomerular filtration rate (eGFR) <30 mL/min/1.73 m² according to 4-variable Modification of Diet in Renal Disease study equation (MDRD, calculated by central laboratory)

Alanine aminotransferase (ALT) or aspartate aminotransferase (AST) $>3x$ ULN at screening

- b. Creatine phosphokinase (CPK) $>3x$ ULN at screening

Note: For all laboratory values, 1 repeat measurement is allowed.

9. Systolic blood pressure >160 mmHg or diastolic blood pressure >100 mmHg at the screening visit or time of randomization (1 repeat allowed). The uneven distribution of these patients across treatment groups could confound the analysis of safety.
10. History of heart failure (New York Heart Association [NYHA] Class III-IV) within 12 months before screening. The uneven distribution of these patients across treatment groups could confound the analysis of safety.
11. Within 3 months of screening, a history of myocardial infarction (MI), unstable angina leading to hospitalization, coronary artery bypass grafting (CABG) surgery, percutaneous coronary interventions (PCI), uncontrolled cardiac arrhythmia, carotid surgery or stenting, stroke, transient ischemic attack (TIA), carotid revascularization, endovascular procedure, or surgical intervention for peripheral vascular disease. The uneven distribution of these patients across treatment groups could confound the analysis of safety.
12. Significant concomitant illness including, but not limited to: cardiac, renal, neurological, endocrinological, hepatic, metabolic, or lymphatic disease, that would adversely affect the patient's participation in the study
13. History of cancer within the past 5 years, except for adequately treated basal cell skin cancer, squamous cell skin cancer, or in situ cervical cancer
14. Participation in a clinical research study evaluating an investigational drug within 30 days or at least 5 half-lives of the investigational drug, before screening, whichever is longer
15. History or evidence of drug or alcohol abuse within 24 months before screening. Additionally, patients who do not agree to limit alcohol intake to no more than 1 drink per day will be excluded.
16. Documented* positive polymerase chain reaction (PCR) or equivalent test based on regional recommendations for COVID-19 or suspected SARS-CoV-2 infection, and:
 - a. Has not recovered from COVID-19 (ie, all COVID-19-related symptoms and major clinical findings which can potentially affect the safety of the patient have not been resolved), and
 - b. Did not have 2 negative results from nucleic acid amplification (PCR) test or equivalent test based on regional recommendations for COVID-19 (at least 48 hours apart) to confirm that the patient is negative for SARS-CoV-2 or, if COVID-19 PCR (or equivalent) testing is not feasible, at least 3 months have transpired since the initial diagnosis
- * Note: Screening for COVID-19 will not be performed as part of eligibility assessments for this study.
17. Members of the clinical site study team and/or his/her immediate family, unless prior approval granted by the sponsor.

18. Pregnant or breastfeeding women.
19. Women of childbearing potential* who are unwilling to practice highly effective contraception prior to the initial dose/start of the first treatment, during the study, and for at least 24 weeks after the last dose. Highly effective contraceptive measures include:
 - a. Stable use of combined (estrogen- and progestogen-containing) hormonal contraception (oral, intravaginal, transdermal) or progestogen-only hormonal contraception (oral, injectable, implantable) associated with inhibition of ovulation initiated 2 or more menstrual cycles prior to screening;
 - b. Intrauterine device (IUD); intrauterine hormone-releasing system (IUS);
 - c. Bilateral tubal ligation;
 - d. Vasectomized partner (provided that the male vasectomized partner is the sole sexual partner of the WOCBP study participant and that the vasectomized partner has obtained medical assessment of surgical success for the procedure); and/or
 - e. Sexual abstinence†, ‡

*WOCBP are defined as women who are fertile following menarche until becoming postmenopausal, unless permanently sterile. Permanent sterilization methods include hysterectomy, bilateral salpingectomy, and bilateral oophorectomy.

A postmenopausal state is defined as no menses for 12 months without an alternative medical cause. A high follicle-stimulating hormone (FSH) level in the postmenopausal range may be used to confirm a postmenopausal state in women not using hormonal contraception or hormonal replacement therapy. However, in the absence of 12 months of amenorrhea, a single FSH measurement is insufficient to determine the occurrence of a postmenopausal state. The above definitions are according to the Clinical Trial Facilitation Group (CTFG) guidance. Pregnancy testing and contraception are not required for women with documented hysterectomy or tubal ligation.

†Sexual abstinence is considered a highly effective method only if defined as refraining from heterosexual intercourse during the entire period of risk associated with the study drugs. The reliability of sexual abstinence needs to be evaluated in relation to the duration of the clinical trial and the preferred and usual lifestyle of the patient.

‡Periodic abstinence (calendar, symptothermal, post-ovulation methods), withdrawal (coitus interruptus), spermicides only, and lactational amenorrhea method (LAM) are not acceptable methods of contraception. Female condom and male condom should not be used together.

20. Patients with a history of serious hypersensitivity reactions to evinacumab or to any of the excipients.
21. Has received a COVID-19 vaccination (initial series or booster) within 1-week of planned start of study medication or for which the planned COVID-19 vaccinations would not be completed 1-week prior to start of the study.

7.3. Premature Withdrawal from the Study

A patient has the right to withdraw from the study at any time, for any reason, and without repercussion.

The investigator and/or sponsor have the right to withdraw a patient from the study if it is no longer in the interest of the patient to continue in the study, or if the patient's continuation in the study places the scientific outcome of the study at risk (eg, if a patient does not or cannot follow study procedures). An excessive rate of withdrawals would render the study uninterpretable; therefore, unnecessary withdrawal of patients should be avoided.

Patients who are withdrawn prematurely from the study will be asked to complete the early termination visit, as described in Section [9.1.2](#).

Rules for discontinuation of study treatment (permanent or temporary) are discussed in Section [8.3.2](#).

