4. ENDPOINTS

4.1. Primary Efficacy Endpoint

The primary efficacy endpoint is the proportion of patients with at least 1 positively adjudicated AP episode during the 52 weeks of the DBTP (intent-to-treat [ITT] estimand - binary).

The ITT estimand – binary used for the primary efficacy analysis is defined as the treatment policy strategy, specifically the occurrence of intercurrent events (ie adherence to study treatment and subsequent therapies) is irrelevant; the value for the primary efficacy endpoint is used regardless of whether or not intercurrent events occur (Section 11.4.3.1).

Note: AP is defined in Section 5.2.1.

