8.3.2. Study Drug Discontinuation

Patients who permanently discontinue from study drug should be encouraged to remain in the study. Those who agree and do not withdraw from the study will be asked to return to the clinic for all remaining study visits and assessments per the visit schedule, especially the week 52 visit, including the off-drug follow-up visits ([Table 1](#) and [Table 2](#)).

Patients who permanently discontinue from study drug and who opt to withdraw from the study (ie, are unable or unwilling to attend the study visits as described above) will be asked to complete study assessments at an early termination (ET) visit, per Section [9.1.2](#). These patients will then enter the off-drug treatment follow-up period, and should be followed for at least 20 weeks from the last dose of study drug or up to recovery or stabilization of any AE to be followed-up as specified in this protocol, whichever comes last. The off-drug follow-up period will include 2 in-clinic visits with assessments as specified under visit 16 and visit 17 ([Table 2](#)).

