11.4.3. Efficacy Analyses

11.4.3.1. Primary Efficacy Analysis

Intent-to-Treat Estimand – Binary

The ITT estimand – binary used for the primary efficacy analysis is defined as the treatment policy strategy, specifically:

- A. The patient population is defined as the ITT population (Section 11.3.1.1).
- B. The primary efficacy endpoint is defined in Section 4.1.
- C. The intercurrent events of interest are the administration of study treatment and the administration of subsequent therapies. The interruption of study treatment and the change in subsequent therapies are ignored, and the value for the primary efficacy endpoint is used regardless of adherence to study treatment and subsequent therapies.
- D. The analysis method of logistic regression will yield the population-level summary of odds ratio and 95% confidence interval (CI) for each study treatment group, and p value for treatment comparisons.

Statistical Analysis

The primary efficacy comparison will evaluate the evinacumab 20 mg/kg IV treatment group versus placebo using the primary efficacy endpoint of the proportion of patients with at least 1 positively adjudicated AP during the 52 weeks of DBTP (ITT estimand - binary). The primary efficacy endpoint will be analyzed in the ITT population using the method of logistic regression, and the model will include at least treatment group, and number of historical AP episodes within the previous 24 months. The evinacumab group will be compared to the placebo group, with odds ratio and 95% CI provided for each treatment group. The statistical testing of the treatment group comparison for the primary measure will be evaluated at a 2-sided significance level of 0.049.

Every effort will be made for patients to return to the clinic for the week-52 assessment of the efficacy endpoints (regardless of study drug administration) to minimize missing data that was required to be collected in this protocol.

For ET patients who did not complete the week-52 efficacy assessment, the missing primary endpoint will be imputed according to the following rules:

- Early termination patients who had a primary endpoint event during the 52-week DBTP will be analyzed as “event occurred.” (Observed, thus no imputation)
- Direct imputation of missing primary endpoint at the week-52 visit:
 - Patient deaths prior to week 52 that are adjudicated to be AP-related will be included as “event occurred.”

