 - Remaining ET patients (including non-AP deaths) across both treatment groups will be imputed to the average placebo score (estimated placebo event rate).
- Imputed scores along with observed patient data will be utilized in the logistic regression analysis.

Robustness of the primary analysis statistical methods will be assessed through sensitivity analyses detailed in the SAP, including a tipping point analysis, observed-case analysis (ie ITT population in the absence of imputed primary endpoint data), and an on-treatment analysis (ie mITT patient population using the primary endpoint collected during the efficacy treatment period [on-treatment estimand]).

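### Protocol 7.3 allows removal from the study for not following procedures, which can end acute pancreatitis follow-up before week 52 although the primary estimand needs that outcome

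*Protocol*

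**What the plan says.** Protocol 7.3 gives the investigator and sponsor two grounds for withdrawing a patient from the study: the patient's own interest, and the case where "continuation in the study places the scientific outcome of the study at risk (eg, if a patient does not or cannot follow study procedures". It adds that a high withdrawal rate would make the study uninterpretable and that "unnecessary withdrawal of patients should be avoided". It sets no criteria for what is unnecessary. Stopping study drug is a separate matter, which 7.3 refers to 8.3.2.

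Other sections ask for retention:

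- Protocol 4.1: "the value for the primary efficacy endpoint is used regardless of whether or not intercurrent events occur". Protocol 11.4.3.1 repeats this: "the value for the primary efficacy endpoint is used regardless of adherence to study treatment and subsequent therapies".
- Protocol 6.1: "Every effort will be made to keep patients in the study and to collect the week 52 visit data", including for patients no longer on drug.
- Protocol 8.3.2: "Patients who permanently discontinue from study drug should be encouraged to remain in the study".

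A patient withdrawn early is asked to attend an early termination (ET) visit and then enters off-drug follow-up (7.3 and 9.1.2). The only stated minimum is in 8.3.2, written for patients who stop drug and choose to leave: they "should be followed for at least 20 weeks from the last dose of study drug", or longer if an adverse event is still being followed.

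Protocol 11.4.3.1 treats the primary endpoint of an ET patient without a week-52 assessment as missing. Events already observed count as events, and so do deaths adjudicated as AP-related. For the rest: "Remaining ET patients (including non-AP deaths) across both treatment groups will be imputed to the average placebo score (estimated placebo event rate".

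**The concern.** A treatment-policy analysis needs the outcome after a patient departs from the plan. The only example in 7.3 makes procedural non-adherence an accepted reason to stop following the patient altogether. All doses are infused in the clinic (8.8.4), so failing to follow procedures can include missed infusion visits. The same patient is then one whom 6.1 and 8.3.2 want retained and whom 7.3 allows to be removed.

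The removal is discretionary and takes place after randomization. Patients who do not keep to visits or other procedures may plausibly differ in AP risk, so the missingness could be informative; the documents do not show this. On the planning rates, 60 per arm gives about 18 placebo events (60 x 0.30) and about 4 evinacumab events (60 x 0.06), so a few lost outcomes carry weight.

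**Working it through.** **1. When follow-up falls short.** Dosing visits run every 4 weeks from week 0 to week 48, which is 13 visits (Protocol Table 1). With a last dose at week L, the minimum follow-up ends at week L + 20.

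- L = 32: 32 + 20 = 52, which just reaches week 52.
- L = 28: 28 + 20 = 48, which is 4 weeks short.
- L = 0: 0 + 20 = 20, which is 32 weeks short.

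The minimum ends before week 52 for last doses at weeks 0 to 28, which is 8 of the 13 dosing visits. This assumes that the 8.3.2 minimum also applies to patients removed under 7.3; no other minimum is given.

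**2. The plan's own power figure.** Inputs from Protocol 11.2: 60 per arm, 30% against 6%, two-sided alpha 0.049, 5% non-evaluable, 90% power. The test is not named. Fisher's exact test with 60 x 0.95 = 57 evaluable per arm gives 90.5%, which reproduces the stated figure. The pooled two-proportion formula gives 92.5% at 57 per arm and 93.7% at 60.

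**3. Illustration of size.** Suppose a share w of the whole evinacumab arm is withdrawn before any event and scored at 0.30. Placebo withdrawals scored at the placebo rate leave that arm at 30%. The analysed evinacumab rate is

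p_E = 0.06 x (1 - w) + 0.30 x w = 0.06 + 0.24w.

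Version A treats imputed values as ordinary binary outcomes (pooled formula, 60 per arm). Here d = 0.30 - p_E, p_bar is the mean of the two rates, S0 = sqrt(2 x p_bar x (1 - p_bar)/60), S1 = sqrt((0.21 + p_E x (1 - p_E))/60), z = 1.969, and power = Phi((d - z x S0)/S1).

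Version B treats imputed values as fixed scores of 0.30 (unpooled normal approximation). The evinacumab variance is v = (1 - w) x 0.06 x 0.94 + w x (1 - w) x 0.24^2, and power = Phi(d/sqrt((0.21 + v)/60) - z).

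| w | Patients of 60 | p_E | d | Power A | Power B |
|---|---|---|---|---|---|
| 0 | 0 | 6.0% | 24.0 points | 93.7% | 94.9% |
| 5% | 3 | 7.2% | 22.8 points | 90.3% | 92.7% |
| 10% | 6 | 8.4% | 21.6 points | 85.9% | 89.9% |
| 15% | 9 | 9.6% | 20.4 points | 80.6% | 86.4% |

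The two versions start from different values at w = 0 because one pools the variance and the other does not, so each column should be read downward. The protocol does not say how a fractional score enters the logistic regression, so both are shown.

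The values of w are assumptions. The calculation gives withdrawn patients the average risk of their arm, so it shows dilution from the imputation and does not measure bias from informative withdrawal.

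**The case against.** There is a fair case that this is minor.

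- **The example concerns study procedures, while the estimand's intercurrent events concern study treatment and later therapies.** This stands. A reader might infer that 7.3 tells sites to remove patients who stop drug, or that it flatly contradicts the estimand. It does neither: 8.3.2 keeps patients who stop drug, and an estimand says which outcomes count without itself preventing missing data. The overlap is with procedural lapses, missed infusion visits among them.
- **The clause is a reserved right, and 7.3 discourages unnecessary use of it.** This also stands, but there are no criteria, and the one example presents procedural non-adherence as a sufficient reason.
- **Observation does not end at once.** There is an ET visit and off-drug follow-up, adverse events are recorded to the end of study (10.1.1), and observed events and AP-related deaths are counted. For last doses from week 32 on, the minimum follow-up reaches week 52. The gap is confined to earlier last doses.
- **Tipping-point and observed-case analyses are planned (11.4.3.1).** They show how far the result depends on the missing outcomes. They do not recover them.
- **The power loss belongs to the imputation rule.** Correct. That rule covers every ET patient, whatever the reason for leaving, so a reader who charges the whole loss in the table to 7.3 would go beyond the documents. At 5%, the non-evaluable rate already allowed for, power stays at the stated 90%.

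**Conclusion.** The point holds as a design weakness of limited size. Section 7.3 offers a discretionary route by which a primary outcome that could have been collected becomes an imputed one, and this fits poorly with 4.1, 6.1, 8.3.2 and 11.4.3.1. The gap arises for last doses at weeks 0 to 28, on the assumption that the 20-week minimum governs.

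The effect on power cannot be stated, because the number of such withdrawals is unknown. The illustration shows no shortfall from 90% at a 5% share. At 10% and 15%, power is 85.9% and 80.6% with binary scoring, or 89.9% and 86.4% with fixed scores. A reader might also infer that the trial's reported result will be biased. The documents do not support this: no difference in AP risk is shown, the study was administratively discontinued (SAP 1), the protocol's efficacy analyses and hypothesis test are dropped (SAP 1.2.4 and 5.7), and missing efficacy data are not imputed (SAP 6.2). The correction matters mainly for the protocol as a design and for any later study that reuses this text.

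**What to change.** In Protocol 7.3, state that not following study procedures is not by itself a reason to end AP outcome follow-up. Add that patients whom the investigator or sponsor withdraws on this ground continue AP ascertainment to week 52, for example by phone or review of records, unless they withdraw consent, are lost to follow-up, die, or continuing is not in their interest. This is practical because the endpoint rests on investigator reports and adjudication (9.2.2.1), not on a measurement that needs a clinic visit. Reconcile 7.3 with 4.1, 6.1, 8.3.2 and 11.4.3.1 so that all give sites the same instruction.

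Neither the patient's right to withdraw nor the ground of the patient's own interest is affected, so the clause can be narrowed without being deleted. The cost is a short change to the text and some continued contacts with poorly adherent patients.
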